- Economically or Educationally Disadvantaged Persons

Other Resources:

- UKMC Residents or House Officers [see [requirement of GME](#)]
- [Non-English Speaking](#) [see also the E-IRB Research Description section on this same topic]
- [International Citizens](#) [DoD SOP may apply]
- [Military Personnel and/or DoD Civilian Employees](#)

Assessment of the potential recruitment of subjects with impaired consent capacity (or likelihood):

Check this box if your study does NOT involve direct intervention or direct interaction with subjects (e.g., record-review research, secondary data analysis). If there is no direct intervention/interaction you will not need to answer the impaired consent capacity questions.

Does this study focus on adult subjects with any conditions that present a high *likelihood* of impaired consent capacity or *fluctuations* in consent capacity? (see examples below)

Yes No

If Yes and you are not filing for exemption certification, go to "[Form T](#)", complete the form, and attach it using the button below.

Examples of such conditions include:

- Traumatic brain injury or acquired brain injury
- Severe depressive disorders or Bipolar disorders
- Schizophrenia or other mental disorders that involve serious cognitive disturbances
- Stroke
- Developmental disabilities
- Degenerative dementias
- CNS cancers and other cancers with possible CNS involvement
- Late stage Parkinson's Disease
- Late stage persistent substance dependence
- Ischemic heart disease
- HIV/AIDS
- COPD
- Renal insufficiency
- Diabetes
- Autoimmune or inflammatory disorders
- Chronic non-malignant pain disorders
- Drug effects
- Other acute medical crises

Attachments

SUBJECT CHILDREN

0 unresolved
comment(s)**SECTION 1. Risk Level**

Complete this section and include it with your IRB application submission. *In Kentucky, a child is an individual less than 18 years of age unless the individual is legally emancipated.*

Note: the explanation(s) you are being asked to provide in Section 1 correlate(s) to the risk level you selected in the Risk Level section.

Minimal risk means that the probability and magnitude of the harm or discomfort anticipated in the research are not greater in and of themselves than those ordinarily encountered in daily life of a healthy child or during the performance of routine physical or psychological exams or tests.

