FOR FDA REGULATED RESEARCH: Based on the 2013 FDA final rule Subpart D, a placebo control arm of a clinical trial must be approved under either [Risk Category 1](#), [Risk Category 3](#), or [Risk Category 4](#). FDA does not consider administration of a placebo to offer a prospect of direct benefit to an individual subject under Subpart D, Risk Category 2 [[21 CFR 50.52](#)].

Not involve greater than minimal risk.

In the Risk Level section of the IRB Application you indicated your research does not involve greater than minimal risk.

A. Explain why your research does not involve greater than minimal risk:

The addition of the band to a standard treatment program does not increase the risk of any adverse events.

SECTION 2. Assessment and Evaluation of the Risks

For details, refer to the UK IRB's [Policy on Children in Research](#).

A. Provide justification for the participation of children as research subjects in your study.

Children under the age of 18 are more susceptible to the condition being studied.

B. Has this research been conducted in adults? Yes No

If yes, is there any indication that the proposed research would benefit, or at least not be harmful to children?

The training is typically done on all subjects, the use of the bands has been used in healthy populations both young and old without incident.

C. Indicate how many children you propose to enroll in the study:

Note: Whenever possible, involve the fewest number of children necessary to obtain statistically significant data which will contribute to a meaningful analysis relative to the purpose of the study.

Justify this
number:

At the onset, the study is open to all subjects ages 15-40. We except that only 10-15 subjects will fall under the age of 18.

D. Check all that apply:

My research involves children 6 years of age or older.
 My research involves children under 6 years of age.

Indicate how assent will be solicited by selecting all that apply:

Affirmative assent will be solicited from: All Children Sub-group of children None of the children

I am requesting waiver of the requirement for assent from: All Children Sub-group of children N/A

Indicate justification for waiving assent for these children: (Check all that apply)

1. The intervention or prospect involved in the research holds out a prospect of direct benefit that is important to the health or well-being of the child/children and is available only in the context of the research.

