 2. The children are not capable of providing assent based on the age, maturity, or psychological state.
 3. The capability of the children is so limited that they cannot reasonably be consulted
 4. Other (explain)

** If you checked question 3, please explain:

** If you checked question 4, please explain:

E. Unless you are requesting a waiver of the requirement for assent for ALL children, you must answer "yes" to at least one of the following two statements.

Note: All assent forms or scripts must be attached to the "Informed Consent" section of this application. Be sure to save your responses in this section first.

For Children 6-11:

Affirmative assent will be obtained verbally. I have attached an assent script for obtaining verbal assent for IRB review.

Yes No

For Children 12-17:

The children will document assent by signing an assent form, or provide assent verbally if approved by the IRB, depending on the circumstances outlined in the application. I have attached an assent form or script for IRB review.

Yes No

F. Explain how study personnel will evaluate dissent (e.g., behaviors that would indicate the child does not want to participate such as moving away, certain facial expressions, head movements, etc.). If your study involves only children under 6 years of age, enter "N/A" below.

If the child does not seem to want to participate, any form of negative body language or hesitation would be taken into consideration prior to having s/he sign any consent forms

G. Describe how parental permission will be obtained.

Parents will sign the consent form and the child will sign the assent form

I have attached a parental permission form for IRB review. Yes No

Parental permission forms must be attached in the "Informed Consent" section of this application. Be sure to save your responses in this section first.

Note that for Risk Category 3 or Risk Category 4 where research involves more than minimal risk without the prospect of direct benefit to the individual child, the permissions of both parents is required unless one parent is deceased, unknown, incompetent, or not reasonably available OR or only one parent has legal responsibility for the care and custody of the child.)

I am requesting

- The permission of both parents unless one parent is deceased, unknown, incompetent, or not reasonably available or when only one parent has legal responsibility for the care and custody of the child. (required for Risk Category 3 or Category 4 Research).

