Data collection for all subjects will be conducted in the BioMotion Laboratory the CCTS and the MRISC at the University of Kentucky. Testing sessions may last approximately 6 hours depending on scheduling of the MRISC and CCTS procedure room. Subjects will be requested to wear sports clothes (e.g. athletic shoes, shorts, and t-shirt). The first data collection will occur before they start the treatment program and will consist of all study procedures except running and jumping. The second data collection will occur before surgery and will consist of measuring intake scales, quadriceps strength, and walking gait. Following surgery, subjects will be administered the intake questions at regular intervals to help the study staff assist them with attending their physical therapy visits. We will then administer all study interventions except running and jumping between 3-4 months after surgery. The last data collection will occur 6-7 months after surgery and will include quadriceps strength assessment, walking and running gait, step down test performance and jumping. The timing of testing maybe delayed by upto 1-2 weeks if the subject is out of town for vacation or illness.

Research procedures for the muscle biopsy and MRI arm of the study will follow procedures already within another study focused on subjects with an ACL tear and reconstruction (11-0388):

Patients will be asked to stop taking aspirin 5 days and NSAIDS 3 days prior to starting the study. Study personnel will confirm that they have not taken aspirin or NSAIDS prior to the start of the muscle biopsy. Those who do not will be excluded from the additional analysis.

Muscle Biopsy: A muscle biopsy sample will be obtained from the vastus lateralis of both thighs in individuals before surgery and again when they have been cleared to practicing drills for their sport or are in a maintenance phase of physical therapy. The muscle biopsy procedure will proceed as follows for each subject taking approximately 15 minutes.

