Describe why potential benefits are reasonable in relation to potential risks. If applicable, justify why risks to vulnerable subjects are reasonable to potential benefits.

Risks strength assessment and training are minimal and include muscle or joint soreness during and after the training session. The training program proposed has been shown to be safe within the population to be tested [2, 6]. Subjects will be closely monitored by the research team during data collections. The lab is only accessible with badge access and remains locked.

Muscle Biopsy. Potential risks involved within the study procedures include those during the muscle biopsy and exercise testing. With the muscle biopsy procedure, there is a risk of bleeding, bruising, pain, infection, and scarring of the skin. Bleeding could rarely result in development of a hematoma. Pain and soreness usually resolves within 24-48 hrs post-procedure. Numbness of the skin near the biopsy site may occur and is usually temporary, but this numbness may persist indefinitely. An allergic reaction to the anesthetic also may occur but is rarely seen.

Blood draws. There is a risk of local pain, soreness, bleeding, bruising and swelling, as well as lightheadedness, dizziness and rarely, fainting and/or a local infection.

MRI. The risks from MRI are minimal. The images taken will be of the quadriceps muscle and used to construct muscle fibers and determine muscle volume. They are used only for research and are not read for any clinical interpretation.

Possible Risk/Side Effect from MR Scanning How often has it occurred? How serious is it? Can it be corrected?

Claustrophobia It occasionally occurs Can be treated Yes, volunteer is removed from the magnet

Loud noise It is expected to occur Not serious Yes, participants wear ear protection

Subjects will not receive any direct benefit from participating in this study. Risks to the subjects are minimal as strength is the primary outcomes being measured. If patients choose to participate in the study, the benefit to general knowledge may be great.

Available Alternative Opportunities/Treatments

Describe alternative treatments or opportunities that might be available to those who choose not to participate in the study, and which offer the subject equal or greater advantages. If applicable, this should include a discussion of the current standard of care treatment(s).

There is no alternative treatment to this study other than not participating in the study.

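### The minimal-risk classification for minors is justified by the band alone, leaves out the biopsies, blood draws and MRI, and is contradicted by the study's own monitoring plan

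*Combined protocol and SAP*

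**What the plan says.** Subject Children, Section 1 (Risk Level) records the declared level: "In the Risk Level section of the IRB Application you indicated your research does not involve greater than minimal risk". Item A asks for the explanation, and the whole answer is: "The addition of the band to a standard treatment program does not increase the risk of any adverse events". The same section prints the standard to be met, namely harm or discomfort "not greater in and of themselves than those ordinarily encountered in daily life of a healthy child", or during routine examinations or tests.

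Data Collection & Research Materials sets out the procedures. Tissue sampling is described as follows: "A muscle biopsy sample will be obtained from the vastus lateralis of both thighs in individuals before surgery and again when they have been cleared". The later occasion is tied to clearance for sport drills or to maintenance therapy. Each biopsy uses local anaesthetic, a scalpel incision through skin and fascia, and a 5 mm needle that removes about 100-200 mg of muscle. Blood is drawn at both biopsy times and one week after surgery, 7.5 mL each time. MRI of the thigh is also planned.

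Potential Risks & Benefits lists bleeding, bruising, pain, infection and scarring from biopsy. It says of numbness near the site that "this numbness may persist indefinitely". It also states: "Subjects will not receive any direct benefit from participating in this study".

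Data and Safety Monitoring gives two risk levels. The Risk Assessment paragraph, printed twice, calls the study minimal risk. The Monitoring Plan says the risks are above minimal and gives that as the reason for using a standing DSMB.

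On permission, the note to Section 2.G says that for research above minimal risk with no prospect of direct benefit to the child, "the permissions of both parents is required unless one parent is deceased" or another listed exception applies. The options below it permit one parent's permission for Category 1 or 2 research. On dissent, Section 2.F says "any form of negative body language or hesitation would be taken into consideration prior to having s/he sign any consent forms".

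**The concern.** A risk classification for children has to cover what will be done to the children. Here the explanation covers the band and omits the most invasive research procedure in the study. The Informed Consent Process text speaks of the biopsies as an addition, so the children's section may simply not have been updated when they came in. The documents do not say so.

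The classification has a practical consequence. It determines whether one parent's permission is enough or both parents' is needed. If the risk level in the Monitoring Plan is the right one, the statement of no direct benefit puts the study under the form's both-parents rule. If the level in the children's section is right, one parent may suffice. The plan asserts both levels, so a reader cannot tell which permission rule governs the minors in this trial.

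**Working it through.** No sample-size, power or error-rate figure is at issue. The check is a comparison of sections plus simple counts.

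**Are minors in scope for biopsy?**
- Eligibility is 15-40 years (Study Population).
- Section 2.C of Subject Children expects 10-15 participants under 18.
- The biopsy text makes no age exception, and none appears elsewhere.
- The Payment section includes MRI and biopsy in what each ACL participant is paid to complete, so biopsy is an expected component.

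**Does the children's section address biopsy?**
- Section 1.A: band only.
- Section 2.B (previous research in adults): training and bands only.
- Sections 2.C to 2.J: no mention of biopsy, blood draw or MRI.

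**What risk level is stated, and where?**

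| Place | Stated level | Reason given |
|---|---|---|
| Subject Children, Section 1 | Not above minimal | The band adds no adverse-event risk |
| Data and Safety Monitoring, Risk Assessment | Minimal | None |
| Data and Safety Monitoring, Monitoring Plan | Above minimal | None; used to justify the DSMB |

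The three statements cannot all stand. The adverse-event attribution scale in Data and Safety Monitoring is defined around the biopsy, so the monitoring section treats as a central hazard the procedure that the children's section omits.

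**What follows for permission?**
- Minimal risk: one parent is permitted.
- Above minimal risk with no direct benefit: both parents, subject to the listed exceptions.

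**Counts**
- Biopsies per participant, maximum: 2 thighs × 2 occasions = 4.
- Biopsies in minors, maximum: 10 × 4 = 40 to 15 × 4 = 60.
- Blood per participant: 3 draws × 7.5 mL = 22.5 mL.
- Minors as a share of 60 participants (Study Population): 10/60 = 16.7% to 15/60 = 25.0%.
- Minors as a share of 55 participants (Project Information): 10/55 = 18.2% to 15/55 = 27.3%.

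The biopsy counts are ceilings. Research Procedures makes procedures depend on equipment, investigator judgement and time. The biopsy text refers to a biopsy and MRI arm, and leaves out of the additional analysis those who do not stop aspirin or NSAIDs.

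**The case against.** The strongest reply is that biopsy risk has been assessed, only elsewhere. Potential Risks & Benefits lists the harms. Records, Privacy, and Confidentiality describes physician performance, follow-up the next day and physician review of the site. The Monitoring Plan assigns a DSMB. This is right as far as it goes: the study does not ignore biopsy risk. But Section 1.A is where the determination for children is made and explained, and the study-level assessment in the Monitoring Plan reaches the opposite conclusion.

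Several stronger readings are tempting, and the documents do not support them.

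- *Minors were enrolled with inadequate permission.* The option selected in Section 2.G cannot be seen in the extracted text. The free text there says parents, in the plural, sign the consent form, so both may already sign. The point is that the selection must be checked.
- *The biopsies certainly exceed minimal risk for a child.* They are hard to fit to the printed standard, but the category is for the IRB to determine. What can be shown is that the reason given does not address them and that the documents disagree on the level.
- *Dissent is never checked at the later biopsy.* Section 2.F ties the check to signing, but Section 2.H can be read as having forms signed at the data collections, and Section 2.I gives the child's needs priority throughout. The wording is ambiguous; absence of a later check is not established.
- *Biopsy data from minors would have to be withdrawn.* Nothing in the documents says so.

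Timing is a fair objection too. Study Population ends enrolment on September 1, 2022, the coversheet gives a document date of 8/30/2024, and the Statistical Analysis section is written in the past tense. Part of the remedy may therefore be retrospective. That limits its protective value but does not remove it: the specimens may be kept indefinitely and reused, so it still matters whether permission matched the risk level.

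**Conclusion.** The point holds in this form. The minimal-risk determination for children rests on a reason that covers only the band, omits the biopsies, blood draws and MRI, and conflicts with the Monitoring Plan. Because no direct benefit is claimed, the unresolved level leaves the governing permission rule unresolved as well.

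The size is bounded by the counts above: at most 4 biopsies per minor and at most 40-60 in all. This assumes that the expected number of minors is reached and that each has every biopsy; 10-15 is an expectation, not an enrolled total. The conclusion also assumes that no age exemption appears in attachments that cannot be seen here. It does not rest on any view of which permission option was selected, or of which risk category is correct. This should be corrected, since it concerns the protection of minors and the correction is modest.

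**What to change.** 1. Reconcile the risk level in Subject Children, Section 1 with both statements in Data and Safety Monitoring, so that one level is stated throughout.
2. Rewrite Section 1.A so that the explanation for children covers biopsy, blood draw and MRI as well as the band. Leave the category to the IRB.
3. Check the parental-permission selection in Section 2.G, and the forms already signed for any minors enrolled, against the resulting category.
4. For any minors still to undergo procedures, state in Section 2.F that dissent is also checked before each biopsy and blood draw.

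The cost is an IRB modification, a file check for about 10-15 families if the expectation was met, and possibly a second parental signature. A few minors may decline a biopsy, which would slightly reduce the tissue available for the muscle-fibre objective.

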The rate of which a person can generate force, jump and hop are important metrics used to determine when a person is ready to return to sport again after surgery such as anterior cruciate ligament reconstruction surgery. These measures require the quadriceps to generate sufficient power quickly. Thus, significant improvements in strength as the result of using air bands during training may yield greater improvements in functional abilities than strength training alone. We aim in this study to show that training with air bands in healthy subjects improves performance in these important functional markers. Validating that this type of training improves functional measures in healthy individuals first will serve as justification of future studies focused in injured populations. Thus, we hypothesize that training with air bands (Kaatsu training) will result in significant gains in rate of torque development, as well as vertical and horizontal hop performance.

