Anterior Cruciate Ligament (ACL) injuries are one of the most common knee injuries with an estimated 300,000 ACL injuries that occur annually in the United States.⁷ Many individuals elect to undergo ACL reconstruction surgery. Although this surgery typically has good short-term clinical outcomes, research has indicated ACL injuries and protracted quadriceps weakness can put individuals at risk for functional deficits and may increase the risk of knee osteoarthritis (OA).^{7,8} ACL reconstruction typically produces good self-reported outcomes regarding knee function and return to sport.^{7,8} However, ACL reconstruction often falls short of its main goals of restoring knee function to pre-injury levels and preventing long-term joint degeneration.⁹ Functional deficits can persist even years out from surgery, and multiple lower extremity symmetry differences have been demonstrated 6 months after surgery, while quadriceps strength often never fully returns to pre-injury status.⁸ Additionally, whether performing this type of training prior to surgical reconstruction will help minimize muscle atrophy following surgery has yet to be assessed. Lastly, little is known of physiological response in the muscle to this type of training in those who have either torn or had their ACL reconstructed. Important changes in muscle fiber type, fibrosis, satellite cell number and muscle volume are unknown but important factors to assess if the treatment has been effective. Due to the ability to train at a low threshold, this type of treatment may prove to be very effective in conditions where individuals have either torn or had their ACL reconstructed.

Objectives

List your research objectives. Please include a summary of intended research objectives in the box below.

The objectives of this study are focused on subjects who have recently torn their ACL and plan on having it reconstructed:

- 1) Evaluate the effect of BFRT on quadriceps strength and knee biomechanics after an ACL reconstruction.
- 2). Identify alterations in quadriceps muscle morphology as the result of BFRT after an ACL reconstruction.
- 3) Determine the effect of BFRT on muscle fiber size and type, and the stem/progenitor cell composition after an ACL reconstruction.

Study Design

Describe and explain the study design (e.g., observational, secondary analysis, single/double blind, parallel, crossover, deception, etc.).

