Continuous participant demographic variables (e.g., age, body mass index (BMI), time since surgery) were summarized with descriptive statistics (e.g., sample size, mean, standard error). Categorical variables (e.g., sex assigned at birth) were summarized with descriptive statistics (e.g., counts and percentages). Summary statistics are also presented by treatment group. A chi-squared test was used to evaluate between-group differences in sex assigned at birth and two-sample *t*-tests were used to evaluate between-group differences in quantitative covariates.

All primary and secondary outcomes were continuous. For each outcome, change scores were calculated as: post-intervention (4-5 months post-surgery) – pre-intervention (baseline pre-surgery). Two-sample *t*-tests were then used to assess between-group differences in change scores. Distributional assumptions of two-sample *t*-tests were assessed using plots of each outcome. An analysis of blinding was performed for each of the participants, the data analysts, and the primary investigator of the study. Chi-square tests (or Fisher's exact tests in the case of small cell counts) were used to identify any association between guesses and treatment group for each of the blinded groups. All analyses were performed using R (R version 4.1.2, R Core Team, 2023) and *p*-values ≤ 0.05 were considered statistically significant.

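### The only outcome comparison is an unadjusted change-score t-test at 4-5 months: valid, but usually less precise than baseline adjustment, and it leaves the 6-7-month strength, walking gait and step-down data without a stated analysis

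*Combined protocol and SAP*

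**What the plan says.** **Analysis.** Under Statistical Analysis, one rule covers all primary and secondary outcomes: "For each outcome, change scores were calculated as: post-intervention (4-5 months post-surgery") minus "pre-intervention (baseline pre-surgery"), compared between arms by a two-sample t-test. No baseline covariate, repeated-measures model or later time point is mentioned. The section's other between-group tests concern covariates and treatment guesses. It names no outcome. The nearest the documents come is under Potential Risks & Benefits: "Risks to the subjects are minimal as strength is the primary outcomes being measured".

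**Schedule.** Data Collection & Research Materials sets out four collections:

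- First: "The first data collection will occur before they start the treatment program and will consist of all study procedures except running and jumping".
- Second, before surgery: intake scales, quadriceps strength and walking gait only.
- Third: "We will then administer all study interventions except running and jumping between 3-4 months after surgery" (I read interventions here as procedures).
- Last: "6-7 months after surgery and will include quadriceps strength assessment, walking and running gait, step down test performance and jumping".

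The Payment section pays separately for a 4-5-month visit and a 6-7-month visit, so these are distinct occasions.

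**The concern.** Two things follow from setting the analysis rule beside the schedule.

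First, strength, walking gait and step-down are measured before treatment and again at 6-7 months, but the plan never compares the arms on the later values. The Background makes that period relevant: "multiple lower extremity symmetry differences have been demonstrated 6 months after surgery, while quadriceps strength often never fully returns to pre-injury status". As written, no planned comparison would show whether a difference seen at the post-intervention visit is still present two or more months later.

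Second, the change score fixes the weight on baseline at one instead of estimating it. In a randomised trial this costs precision whenever the best weight differs from one. The documents give 55 (Project Information) or 60 (Study Population) subjects, so there is little precision to spare on the strength contrast.

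**Working it through.** The documents give no SD, correlation, effect size, power or dropout figure, so there is no stated result to reproduce. The check below rests on assumptions shown as ranges.

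**Inputs.** N = 55, the stated maximum. Equal allocation is assumed, because the ratio is not stated. Correlation ρ between baseline and follow-up is assumed from 0.3 to 0.9. The SD ratio k = baseline SD / follow-up SD is assumed to be 0.8, 1 or 1.25.

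**Variance per subject, in units of the follow-up variance.**

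- Change score: 1 + k² − 2ρk
- Baseline-adjusted: 1 − ρ², times a small-sample cost of 1 + 1/(N − 4) = 1 + 1/51 = 1.0196

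Before the small-sample cost, the change-score variance minus the adjusted variance is (k − ρ)². It is never negative, and it is zero only when k = ρ.

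**Example.** At k = 1 and ρ = 0.5, the change score gives 1 + 1 − 1 = 1.00 and adjustment gives 0.75 × 1.0196 = 0.765. The ratio is 0.765, a reduction of 23.5%.

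**Variance ratio, adjusted / change score, N = 55.**

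| k | ρ = 0.3 | 0.5 | 0.7 | 0.8 | 0.9 |
|---|---|---|---|---|---|
| 1 | 0.663 | 0.765 | 0.867 | 0.918 | 0.969 |
| 0.8 | 0.800 | 0.910 | 1.000 | 1.020 | 0.969 |
| 1.25 | 0.512 | 0.583 | 0.640 | 0.653 | 0.620 |

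With equal SDs the confidence interval is about 13% narrower at ρ = 0.5 (√0.765 = 0.874) and 7% narrower at ρ = 0.7 (√0.867 = 0.931). The single loss in the table, 2%, is at k = ρ = 0.8, where only the small-sample cost remains.

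**Simulation check.** With 28 and 27 subjects, equal SDs and 8,000 runs per correlation, the variance ratios were 0.767, 0.867 and 0.967 at ρ = 0.5, 0.7 and 0.9. For an assumed true difference of 0.5 SD, power with the change score and with adjustment was 45% and 55%, 65% and 72%, and 98.3% and 98.6%.

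**What a 6-7-month strength contrast would deliver.** The 95% CI half-width is t(0.975) × √(4V/N), in follow-up SDs, with k = 1 and V the variance above. The second row assumes 20% loss (55 × 0.8 = 44).

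| N | Adjusted, ρ = 0.5 | Change score, ρ = 0.5 | Adjusted, ρ = 0.7 | Change score, ρ = 0.7 |
|---|---|---|---|---|
| 55 | 0.47 | 0.54 | 0.39 | 0.42 |
| 44 | 0.53 | 0.61 | 0.44 | 0.47 |

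**Running and jumping.** The first and third collections exclude them, and the second does not list them. They exist only at 6-7 months, so no change score can be formed. An unadjusted comparison of levels (V = 1) has a half-width of 0.54 SD at N = 55 and 0.61 SD at N = 44. The difference detectable with 80% power is 0.77 SD and 0.87 SD respectively.

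**Visit window.** The schedule puts the third collection at 3-4 months after surgery. Payment and Statistical Analysis put the post-intervention visit at 4-5 months. The treatment description allows a 1-2-month program extension and the schedule a 1-2-week testing delay. Either may explain part of the gap, but the text does not say so.

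**The case against.** **The gain is assumed.** This is fair. No correlation or SD is given, and the benefit falls to 8% and 3% at correlations of 0.8 and 0.9 with equal SDs, and to nothing or slightly less in one corner of the grid. What stands is the asymmetry: the worst case costs about 2% of variance, while most of the range shows a gain.

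**The analysis may already be done.** The Statistical Analysis section is in the past tense and names the software version. Study Population ends enrollment on September 1, 2022, and the document is dated 8/30/2024. This suggests, without proving, that between-arm results have been seen. If so, replacing the main analysis now would be a results-aware change, and the adjusted model can only be a labelled addition.

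**Persistence at 6-7 months is not a stated aim.** The Objectives give no time point, and the Background remarks describe ACL patients in general. That makes the 6-7-month contrast secondary. It does not explain collecting the data with no stated use.

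**Running, jump and hop.** A reader might infer that the plan omits the analysis of declared outcomes, since the Background says that "jump and hop are important metrics used to determine when a person is ready to return to sport again after surgery". The documents do not support that. No section lists these measures as outcomes, the Objectives do not name them, and the hop hypothesis follows an aim framed for healthy subjects. Nor is it safe to assume complete data. Research Procedures makes testing subject to equipment, time and the investigator's discretion, and the jump description lets the landing type vary. This part is a request for clarification only.

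**Conclusion.** The point holds as one of efficiency and completeness. The stated t-test on change is valid under randomisation; a reader might infer that it is biased or wrong, but nothing in the documents supports that. It is usually less precise than an adjusted model. With N = 55 and equal SDs, adjustment lowers the variance by about 34, 23.5, 13, 8 and 3% at correlations of 0.3, 0.5, 0.7, 0.8 and 0.9. At an SD ratio of 0.8 the effect runs from a 20% gain (correlation 0.3) to a 2% loss (correlation 0.8). All of this rests on assumed correlations and SD ratios, equal arms and a maximum, not analysed, sample size.

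Separately, and without any assumption, the 6-7-month strength, walking gait and step-down values have no stated between-arm analysis.

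The visit-window mismatch is a wording matter between the schedule on one side and Payment and Statistical Analysis on the other. A reader might add the 4-5-month food record as further evidence, but that entry times only the food record and does not define the visit.

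**What to change.** 1. For strength, walking gait and step-down, compare arms with ANCOVA, or a mixed model with arm-by-visit terms, adjusted for the first-collection value. Name that collection explicitly: strength and walking gait are measured twice before surgery, and only the first is stated to precede treatment. Keep the post-intervention contrast as the main one and report the 6-7-month contrast with a 95% CI as secondary.
2. State whether between-arm results had been seen when this was added. If they had, keep the t-test as the main result and label the adjusted model and the 6-7-month contrasts as added. If not, make the adjusted model the main analysis.
3. Say whether running, jump and hop measures are outcomes. If they are reported, compare 6-7-month levels, not gains, as exploratory, and state how many subjects were tested and with which type of jump.
4. Reconcile the post-intervention visit window across the schedule, Payment and Statistical Analysis.

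The cost is SAP wording and modest programming, with no extra testing. The downsides are a slightly more complex model, a few more labelled contrasts, and about 2% in variance if baseline adds nothing beyond the change score.
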